### **8.7.2. Exploratory analysis**

Exploratory analyses addressing potential effect modifiers such as Asthma Control Test measures of disease symptom control, and measures of asthma exacerbation will be addressed. In addition, subanalyses based on length and gestational timing as well as dose of exposure to mepolizumab will be performed. Additionally, stratified analyses based on prenatal diagnosis performed prior to enrollment in the study will be conducted for the primary endpoint. The purpose of this analysis is to address the inherent bias in excluding women at the time of enrollment in the cohort study who have already received prenatal diagnosis of a major birth defects, but including women who have already had a normal result or prenatal diagnosis for major birth defects prior to enrollment. Therefore, the planned stratified analysis will compare the birth prevalence of major birth defects among the subset of women enrolled in the cohorts *prior to* prenatal diagnostic testing for fetal structural anomalies, to the birth prevalence of major birth defects among the subset of women enrolled in the cohorts *after* prenatal diagnostic testing for fetal structural anomalies. Subanalyses excluding chromosomal or known genetic anomalies (based on specific defects categorized by expert based on known genetic etiology) will also be conducted.

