**Table 4 Denominators by Outcome**

Outcome	Denominator
Major Birth Defects Among Live Births	Pregnancies ending in live birth; with exposure in 1 st trimester for mepolizumab cohort, and other comparison groups at least one malformed infant in an individual pregnancy is considered one malformed outcome
Major Birth Defects Among All Pregnancies	Pregnancies with any outcome excluding those lost-to-follow-up; with exposure in 1 st trimester for mepolizumab cohort, and other comparison groups; at least one malformed fetuses/infants in an individual pregnancy is considered one malformed outcome
Spontaneous Abortion	Pregnancies enrolled in the study prior to 20 weeks' gestation with at least 1 follow-up data collection point after enrollment date. Exposure can occur any time in pregnancy prior to event.
Preterm Delivery	Pregnancies enrolled prior to 37 weeks gestation and ending in at least one live born infant; excluding twins or higher order multiples due to inherent higher risk of preterm birth in multiples. Exposure can occur any time in pregnancy prior to event.
Small for Gestational Age Infants	Pregnancies ending in at least one live born infant; excluding twins or higher order multiples due to the inherent higher risk of reduced birth size in multiples. Exposure can occur any time in pregnancy prior to event.
Still Birth	All pregnancies, excluding lost-to-follow-up. Exposure can occur any time in pregnancy prior to event.

Coding of outcomes is performed by the study staff using the definitions provided in the protocol. The primary source of information on exposure and outcome is the participant. Validation of study outcomes is performed using medical records. In the case of discrepancies in the two sources of report, the participant is recontacted to determine if the discrepancy can be resolved, and an SOP for adjudicating these decisions has been developed.

Missing values for the critical data for PPD studies are typically very few and nearly always less than 10%. There is generally no need to include imputation strategies; however, depending on the prevalence of missingness, sensitivity analyses will be conducted. These will be documented in the DAP.

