## 8.7. Data analysis

### 8.7.1. Essential analysis

A detailed Data Analysis Plan will be prepared and finalised prior to the conduct of any study analysis or reporting.

*Primary Endpoint:* The primary endpoint will be major structural defects among live born infants. The primary comparison will be between the first-trimester mepolizumab-exposed group and the treated disease cohort.

Secondary comparisons for major birth defects will be conducted with the denominator including all pregnancies ending in live birth, spontaneous abortion, stillbirth or elective termination, excluding lost-to-follow-up, comparing first-trimester mepolizumab-exposed to the treated disease cohort.

Additional secondary comparisons will be made between the first-trimester mepolizumab-exposed group and the treated asthma and non-asthmatic cohort. A tertiary objective of the study is to descriptively compare the rate of major birth defects in the mepolizumab-exposed pregnancies, and control groups to external data from the Centers for Disease Control and Prevention (CDC) Metropolitan Atlanta Congenital Defects Program (MACDP), a population-based birth defects surveillance program ([Centers for Disease Control and Prevention](#), 1998).

*Secondary Endpoints:*

Preterm Delivery: After exclusion of twins or higher order multiples, the rate of pregnancies ending in live birth <37 weeks' gestation will be compared between the mepolizumab group enrolled and exposed anytime in pregnancy prior to 37 weeks' gestation and the treated disease and non-asthmatic cohorts enrolled prior to 37 weeks' gestation.

Small for Gestational Age Infants: After exclusion of twins or higher order multiples, the proportion of pregnancies ending in a live born infant  $\leq 10^{\text{th}}$  centile of birth

weight for gestational age and sex will be compared between the mepolizumab-exposed group and the treated disease and non-asthmatic cohorts.

Spontaneous Abortion: For those women in all three cohorts who enrolled in the study prior to 20 weeks' gestation, the rate of spontaneous abortion accounting for left truncation will be compared between those in the mepolizumab group enrolled and exposed any time in pregnancy prior to 20 weeks' gestation and the treated disease and non-asthmatic cohorts.

Stillbirth: The rate of pregnancies ending in stillbirth will be compared between those in the mepolizumab-exposed group and the treated disease and non-asthmatic cohorts.

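### The prenatal-testing analysis in 8.7.2 contrasts women by enrolment timing, so it does not show whether, or in which direction, the primary mepolizumab RR is biased

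*Protocol*

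**What the plan says.** Protocol 8.7.1 defines the primary analysis: "The primary endpoint will be major structural defects among live born infants", and "The primary comparison will be between the first-trimester mepolizumab-exposed group and the treated disease cohort". The eligibility criteria in 8.2 bar a woman from any cohort if she first makes contact after a prenatal diagnosis of a major defect. A woman whose test was normal may still enrol, and Table 5 (8.6.3) allows enrolment as late as 32-34 weeks.

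Section 8.7.2 recognises the consequence. It announces that "stratified analyses based on prenatal diagnosis performed prior to enrollment in the study will be conducted for the primary endpoint" and gives the reason: "The purpose of this analysis is to address the inherent bias in excluding women at the time of enrollment in the cohort study" who already have such a diagnosis, while women with a normal result are admitted. The sentence that then defines the analysis reads "the planned stratified analysis will compare the birth prevalence of major birth defects among the subset of women enrolled in the cohorts" before structural testing, "to the birth prevalence of major birth defects among the subset of women enrolled in the cohorts" after it. It names no comparison of exposed with unexposed women.

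**The concern.** The stated aim and the stated contrast do not match. Women enrolled after testing will show fewer defects, because those with a detected defect were turned away. This distorts the primary RR only if Cohorts 1 and 2 contain different proportions of such women. A contrast of early with late enrollees, taken over the cohorts, does not look at that. It could be reported as having dealt with the bias while the primary RR still carried it, in an unknown direction.

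Unequal timing is possible on the protocol's own account. Section 8.5 expects mepolizumab users typically to enrol once they know they are pregnant, and makes no matching statement about Cohort 2. The other route to control is adjustment: 8.3.3 lists prenatal testing, with its timing and results, among the covariates. That route is unlikely to be open, as the event count below shows.

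**Working it through.** **Inputs.** From the protocol: 3% baseline defect prevalence, and 180 exposed and 270 unexposed analysable pregnancies (8.5, Table 3); a minimum of 30 events for adjusted logistic regression (8.7.1). Assumed, because the protocol gives no figures: the share of each cohort enrolled after testing (l1, l2), and the share d of defects that testing would detect and so bar from later enrolment. The illustration takes d to be the same in both cohorts. It also takes detected defects among before-testing enrollees to end in live birth; if some end in termination, the bias in the live-birth endpoint is smaller.

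**The plan's own figure.** Table 3 states a minimum detectable RR of 3.0. With a pooled-variance normal approximation, two-sided 0.05:
- pooled p = (180×0.09 + 270×0.03)/450 = 0.054
- SE = √[0.054×0.946×(1/180 + 1/270)] = 0.0217
- z = 0.06/0.0217 − 1.96 = 0.80, so power is 78.8%, and the minimum RR at 80% power is 3.04

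The stated 3.0 is reproduced and is not in dispute.

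**Size of a spurious RR when the true RR is 1.** To a close approximation, RR = (1 − l1·d)/(1 − l2·d).

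| d | l1 = 30%, l2 = 60% | Shares reversed | Equal shares |
|---|---|---|---|
| 0.30 | 0.91/0.82 = 1.11 | 0.90 | 1.00 |
| 0.40 | 0.88/0.76 = 1.16 | 0.86 | 1.00 |
| 0.50 | 0.85/0.70 = 1.21 | 0.82 | 1.00 |

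**What the planned contrast would show.** Take d = 0.40 and keep the exact denominator. Prevalence after testing is 0.03×0.6/(1 − 0.03×0.4) = 1.82%, so the early/late ratio is 3.00/1.82 = 1.65. That ratio does not change with the mix of enrolment by cohort, but the exposed/unexposed RR does:

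| After testing, Cohort 1 / Cohort 2 | Early/late ratio | Exposed/unexposed RR |
|---|---|---|
| 30% / 30% | 1.65 | 1.00 |
| 60% / 30% | 1.65 | 0.87 |
| 30% / 60% | 1.65 | 1.15 |
| 20% / 70% | 1.65 | 1.27 |

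(The 1.15 here and the 1.16 above differ only because the first formula ignores the small loss from the denominator.) The contrast is also nearly blind to a real effect: with equal timing and a true RR of 1, 2 or 3, the pooled early/late ratio is 1.65, 1.64 or 1.62.

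**Could adjustment take over?** Expected defects in Cohorts 1 and 2 are 450×3% = 13.5 with no effect, and 180×9% + 270×3% = 24.3 at RR 3. Both fall short of 30. If the event rule were read over all three cohorts, with Cohort 3 assumed also to have 270 pregnancies at 3%, the totals would be 21.6 and 32.4. Only a threefold effect would pass.

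**What the stratified comparison can deliver.** In each stratum before-testing is compared with before-testing, and after-testing with after-testing. In the illustration this gives 3.00/3.00 and 1.82/1.82, so the RR is 1.00 in both. Precision inside a stratum is low (same formula as above):

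| Stratum share of cohort | n exposed / unexposed | Power for RR 3 | Minimum RR | Exposed defects expected at RR 1 |
|---|---|---|---|---|
| 30% | 54 / 81 | 33% | 5.6 | 1.6 |
| 50% | 90 / 135 | 50% | 4.2 | 2.7 |
| 70% | 126 / 189 | 64% | 3.6 | 3.8 |

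**The case against.** The strongest reply is that the early/late contrast is informative. Its ratio is about 1/(1 − d), so it estimates d, and l1 and l2 are simple counts from enrolment and test dates. Together they give the direction and size of the bias. This stands against any claim that the planned analysis is useless. But 8.7.2 does not plan the counts by cohort, and an estimate of d from about 13.5 defects would be weak.

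Second, announcing stratified analyses for the primary endpoint could imply a comparison of cohorts within strata, and a data analysis plan with table shells is promised. That reading is open from the first sentence, but the defining sentence then fixes a different contrast. The point concerns what the protocol fixes, not what it leaves to the later plan.

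Third, nothing shows that Cohort 2 enrols later. Section 8.2 has comparison women coming through the same referral services, and 8.5 expects some enrolment after 20 weeks in every cohort. This stands: a reader might infer that the primary RR is known to be biased, and the documents do not support that. The illustrated RRs are also small beside the detectable RR of 3.0 and the upper bound of 2.8 in Table 3.

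Finally, a reader might extend the criticism to the all-pregnancy comparison, whose denominator is "the denominator including all pregnancies ending in live birth, spontaneous abortion, stillbirth or elective termination, excluding lost-to-follow-up", on the ground that an unexamined loss can count only as non-malformed. The documents do not support treating this as a second failed selection check. Section 8.7.1 and Table 4 give it no such role, defects already known prenatally can enter its numerator, and the live-birth rate is already primary. Restricting it to examined losses would condition on work-up that a suspected defect may itself prompt.

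**Conclusion.** The point holds for the prenatal-testing analysis in 8.7.2. As defined, it can show that women enrolled after testing are selected, but alone it neither removes nor signs any bias in the primary RR. The illustrated spurious RRs of 1.11-1.21, or 0.82-0.90 with the shares reversed, are about the size of the 10% change in estimate that 8.7.1 and 8.7.3 treat as confounding, or larger. They rest wholly on assumed enrolment shares and detection rates, and they vanish if the cohorts enrol alike. This is a mismatch between an exploratory analysis and its stated purpose, worth correcting because the remedy is cheap and adjustment is unlikely to be available. It is not evidence that the primary result will be wrong.

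**What to change.** In 8.7.2, add the comparison of major birth defects between Cohort 1 and Cohort 2 within the before-testing and after-testing strata. Pool it by an exact stratified or Mantel-Haenszel RR with its 95% interval, and report it beside the primary crude RR. Tabulate by cohort the number and share enrolled after testing. The early/late contrast can stay as a description of how strong the selection is.

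The cost is wording and one table: the Annex 2 forms already record enrolment date and the dates and results of prenatal tests and ultrasounds. The pooled interval will be somewhat wider than the crude one. Stratum-specific results should be labelled descriptive, given about 33-64% power for RR 3 if a stratum holds 30-70% of the cohort.

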### **8.7.3. General considerations for data analyses**

The general approach to controlling for confounding is to evaluate each relevant confounder for the specific outcome to determine if inclusion of the confounder in a model containing exposure to mepolizumab changes the estimate of the effect of exposure by 10% or more. The confounders will be assessed univariately and those confounders that are identified are incorporated into multivariate analyses as described in the statistical analysis Section 8.7.1. Further details will be contained in the DAP. Control for confounding by indication is addressed by comparison to the treated disease group. However, as described in exploratory analyses in Section 8.7.2, attention to measures of disease symptom control and underlying severity will also be addressed by subgroup and stratified analysis.

### **8.8. Quality control and Quality Assurance**

As noted in Section 8.7, quality control measures are in place throughout the entire period of data collection and data entry. Training and retraining of study staff is monitored per study SOP, and validation of data entry for critical study variables is conducted for 100% of study participant interactions. Data exported for interim and final analyses for this study are checked for logical errors, and range checks are performed. All major birth defect classifications are verified by the study investigators.

Data are reviewed on an interim basis by the VAMPSS external advisory committee. This committee consists of representation from the U.S. Centers for Disease Control and Prevention Center for Birth Defects and Developmental Disabilities, the Eunice Kennedy Shriver National Institute of Child Health and Development, a biostatistician, a consumer representative, and disease-specific specialty representatives. This standing committee meets annually and reviews all interim and final study reports as well as manuscripts that are produced from the study results. The committee comments on the study progress and poses questions that arise which are addressed by the investigators.

Final data sets are cleaned and utilized for preparation of the analyses and study reports. All analyses (coding and output) are reviewed by the lead study statistician and at least one other staff statistician. Study reports are reviewed by the Study Manager and the

Investigators. All data sets and analytic files are archived indefinitely at the PPD [redacted] and analyses can be replicated as necessary.

## 8.9. Limitations of the research methods

Potential limitations of the research methods are as follows:

The study relies on a volunteer sample which may or may not be entirely representative of all women who take mepolizumab during pregnancy. However, for a new product used for a relatively rare condition this is likely one of the only methods of obtaining safety information for pregnancy exposures because of the ability to target key patient and provider groups, particularly physicians who treat patients with more severe asthma, to increase awareness about the study.

It is unknown what the distribution of timing of exposure will be in the mepolizumab-exposed cohort. In the EXPECT registry for omalizumab, pregnancy exposures were predominately limited to the first trimester (Namazy et al, 2015). Therefore, it is possible that the study will only be able to address the risks or safety of exposures that occur in the first four to six weeks of pregnancy before women typically recognize that they are pregnant.

The sample size that is achievable for a new product used for a relatively rare condition limits the power to detect differences, especially for rare outcomes such as major birth defects. The study will also be limited in ability to address increased risks for spontaneous abortion as the highest risk for spontaneous abortion occurs in the gestational weeks prior to when women would typically enroll in the study. However, based on expected gestational timing of enrolment, spontaneous abortion rates in late first trimester and early second trimester will be analyzable.

Strengths of the study design are the ability to build on the referral network of PPD [redacted] member services across the U.S. and Canada to identify mepolizumab-exposed pregnancies as well as appropriate comparison group pregnancies, the PPD [redacted] research groups' track record of excellent subject retention (<5% lost to follow-up). In addition,

the study design allows for appropriate comparison to a treated disease group, and for appropriate attention to confounding or effect modification.

### **8.9.1. Study closure/uninterpretability of results**

In consultation with the Scientific Advisory Committee, discontinuation of the study will be considered at such time as:

- sufficient information has accumulated to meet the scientific objectives of the study
- other methods of gathering appropriate information become achievable or are deemed preferable
- the feasibility of collecting sufficient information diminishes to unacceptable levels because of low exposure rates, poor enrollment, or losses to follow up. Upon initiation of recruitment, the study is expected to continue to recruit for five years with recruitment ranging from 20-55 patients exposed to mepolizumab per year. Regular review of enrollment numbers will be performed and numbers compared to the sponsor's data and other external data on the uptake of mepolizumab to determine if uptake among women of reproductive age is consistent with enrollment rates in the cohort study. One of the sources of these data is the database arm of VAMPSS which represents a large population-based source of information on pregnancy exposures. Enrollment will also be reviewed with respect to key awareness activities.
- If the Sponsor discontinues manufacturing mepolizumab they may withdraw from the study upon written notification.

### **8.10. Other aspects**

None

## **9. PROTECTION OF HUMAN SUBJECTS**

### **9.1. Ethical approval and subject consent**

The study is approved through the PPD [REDACTED] [REDACTED] (Institutional Review Board or IRB). All study participants must agree to the IRB-approved oral consent form at the time of enrollment and before completing the intake interview. Each participant must subsequently sign the IRB-

approved informed consent document in order to continue to participate in the Registry. Each participant is also asked to sign for release of medical information to allow the Registry to obtain information on the pregnancy and the pregnancy outcome from the participant's obstetrician, the hospital of delivery, and any other health care specialist, and for the infant from the infant's pediatrician.

The original oral and signed informed consent documents, and copies of the medical records release forms will be maintained at the Research Center.

Pregnant women under the age of 18 who are eligible for the study and who wish to participate will require written consent of their parent or guardian prior to the initial intake interview and written assent from themselves. Consent/assent forms and study participation materials are available in English or Spanish.

## **9.2. Subject confidentiality**

The Registry makes every effort to assure participant confidentiality within the Registry. Personally identifiable information is maintained in secure files with restricted access limited to only authorized personnel.

Registry Investigators, data collection and management staff reside at the

PPD [REDACTED] located at the PPD [REDACTED]

PPD [REDACTED] These personnel, under the supervision of the Investigators, have access to the physical files and electronic data, have documented completion of human subjects research training, and are listed individually as authorized to have access to the study data on the study IRB-approved research plan.

Sponsor representatives through the Registry Scientific Advisory Committee have access to de-identified summary data as part of the periodic annual review and the final study report. Final study data files for analysis are stripped of identifiers and archived without personal identifiers.

Care will be taken to ensure that no individual participant is identifiable in the data tables published in the Annual Reports, or other presentations or publications.

## **10. MANAGEMENT AND REPORTING OF ADVERSE EVENTS/ADVERSE REACTIONS**

A Safety Management Plan (SMP) will be developed for the study and will provide detailed information on the study specific pharmacovigilance processes and procedures.

This study adopts the following ICH definitions:

*Adverse event: Any untoward medical occurrence in a patient or clinical investigation subject administered a pharmaceutical product and which does not necessarily have to have a causal relationship with this treatment.*

- An AE can therefore be any unfavourable and unintended sign (including an abnormal laboratory finding) symptom or disease (new or exacerbated) temporally associated with the use of a Medicinal Product. For a marketed Medicinal Product, this can also include failure to produce expected benefits (i.e. lack of efficacy, with or without an adverse event), and adverse events associated with circumstances of Overdose whether accidental or intentional, Medication Errors, Abuse or effects of drug withdrawal, or Misuse.

*Serious adverse event: any untoward medical occurrence that at any dose that 1) results in death, 2) is life threatening, 3) requires inpatient hospitalization or prolongs existing hospitalization, 4) results in persistent or significant disability/incapacity or 5) is a congenital anomaly.*

- Medical and scientific judgement should be exercised in deciding whether expedited reporting is appropriate in other situations, such as important medical events that may not be immediately life-threatening or result in death or hospitalisation but may jeopardise the patient or may require intervention to prevent one of the other outcomes listed in the definition above. These should also usually be considered serious. Examples of such events are intensive treatment in an emergency room or at

home for allergic bronchospasm; blood dyscrasias or convulsions that do not result in hospitalisation; or development of drug dependency or drug abuse.

The purpose of the Mepolizumab Pregnancy Exposure Study is to monitor planned and unplanned pregnancies exposed to mepolizumab and to evaluate the possible teratogenic effect of this medication. For mepolizumab exposed pregnancies pre-defined specific pregnancy outcomes that are classified as serious adverse events (SAE's) will be identified and reported. These selected SAEs include Major Congenital Malformation (MCM), spontaneous abortion, still birth and neonatal death. These events will be reported to the sponsor's safety department within 24 hours.

Additionally, for mepolizumab exposed pregnancies, all other adverse events, which are ascertained as part of the routine study data collection, will be abstracted from maternal interviews (and/or from available medical records) by dedicated and trained study staff. Each of the events will be assessed for causal relationship to mepolizumab exposure by a consulting physician with expertise in asthma and allergy treatment of women of reproductive age. This assessment of events will be performed on a monthly basis by the consulting physician. Only those adverse events attributed by the consulting physician to mepolizumab will be reported to the sponsor's safety department within 24 hours.

Any pregnancies in subjects exposed to mepolizumab reported to the PPD retrospectively, after the outcome is known, will not be enrolled and will be referred to the Sponsor. Other ineligible mepolizumab-exposed pregnancies will also be referred to the Sponsor.

If during the study, the PPD investigators become aware of an adverse event explicitly attributed to any known GSK product, this will also be reported to the sponsor's safety department within 24 hours.

The interim and final study reports will include the serious adverse events that are the study endpoints as part of the hypotheses being tested, and a summary of all mepolizumab attributed adverse events. The final study report will additionally include

all adverse events that have been explicitly attributed to any known GSK product reported to the Sponsor.

